Early Mobilization of Older Adults in the Cardiovascular Intensive Care Unit

I. RESEARCH QUESTION

Is an early progressive mobilization program safe, feasible, and effective in older adults in the Cardiovascular Intensive Care Unit (CICU)?

II. HYPOTHESES

1. An early mobilization (EM) program is safe, feasible, and effective in older adults in a Canadian tertiary care academic CICU.
2. Level of function on CICU discharge and time spent lying in bed during hospitalization is associated with health-related quality of life scores and functional status at longer-term follow-up.

III. SPECIFIC AIMS

Aim #1: To determine functional status and longer-term patient-centered outcomes of older adults admitted to the CICU prior to the implementation of the EM program (“pre-intervention” cohort)

Aim #2: To assess the safety and feasibility of an EM program in a Canadian academic tertiary care CICU

Aim #3: To determine the effectiveness of EM at improving the functional status of older adults during CICU admission and improving longer term patient-centered outcomes (“intervention” cohort)

Aim #4: To evaluate the association of daily time spent lying in bed with functional status at CICU discharge and following hospital discharge

Aim #5: To assess the amount of skeletal muscle mass loss during admission for acute cardiovascular disease

IV. BACKGROUND

A. Physical Function and Impairment in Older Adults in the Critical Care Unit

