Older adults (age $60 \geq$ years old) comprise the majority of patients admitted to the CICU.¹ Older adults have a higher burden of prehospital functional impairment, which is an important predictor of morbidity and mortality during and following critical care unit hospitalization.^{2,3} During hospitalization, older adults are at risk for rapid loss of muscle mass and strength from critical illness, immobility, and prolonged bedrest.⁴ As a result, survivors of critical illness frequently develop physical impairments, such as a reduced ability to ambulate and difficulty performing activities of daily living (ADLs), which can endure well-beyond index hospitalization.⁵⁻⁷ Up to 70% of older adults in the critical care unit are unable to return to prehospital levels of activity at discharge and have significant physical impairments that persist months later.⁵ The enduring physical impairments following critical care unit hospitalization can have devastating effects on the ability of older adults to maintain independence and quality of life and also results in increased morbidity and mortality.⁸

B. Early Mobilization in the Intensive Care Unit: Opportunities and Challenges

EM describes progressive mobilization activities that start immediately upon hemodynamic and respiratory stabilization, typically within 24-48 hours of intensive care unit admission.⁵ The objectives of EM is to prevent loss of muscle function, promote rapidity in

mobility recovery, and to maintain or help patients regain prehospital functional capabilities. There is evidence that EM is associated with improvements in muscle strength, physical function, and quality of life in patients admitted to critical care units.^{9, 10} In addition, EM has also been shown to decrease critical care delirium, improve long-term cognitive outcomes, decrease critical care and hospital length of stay, reduce hospital readmissions, decrease long-term mortality, and result in considerable cost savings.^{5, 11-14} The safety of EM programs in critically ill patients has also been established with only rare reports of serious adverse events and catheter dislodgement. The most commonly reported complications are transient physiologic changes.^{15, 16}

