Prior to the implementation of the EM intervention, nurses will ascertain and record the prehospital LOF, admission LOF, and LOF on the day of CICU transfer (Appendix A), but will continue usual mobilization practices. Patients who meet eligibility criteria for the EM intervention will be prospectively enrolled over a 3-month period (“pre-intervention cohort”) by a member of the research team during CICU admission. Informed consent will be obtained by a member of the research team. Following discharge, a member of the research team will review the medical record to extract demographic data (age, sex), comorbid illnesses, primary admission diagnosis, frailty status, adverse events during mobilization (falls, dislodgements, and injuries), mobilization activities, length of critical care unit stay, length of hospital stay, mortality, and discharge location.

Intervention

On admission to the CICU, the patient’s treating nurse will assess the patient for the EM program. Patients participating in the EM program will be assessed for enrolment in our study by a member of the research team and will obtain informed consent during CICU admission (“intervention cohort”). The potential participants are likely to be competent and medically fit to be approached for informed consent as patients who are not medically fit will be excluded from the early mobilization program based on clinical factors, which include hemodynamic criteria.

The EM program consists of a progression of functional activities from LOF 0 (lowest mobility) to 5 (highest mobility). Each LOF has 3 primary activities designed to promote the patient to the next level. The nurse will begin with mobility activities based on the LOF that matches the patient’s current status. The nurse and clinical partner will attempt and/or complete each LOF activity once per shift. Physiotherapy assistance is available if required, although not obligatory. Nurses will also provide documentation and education to patients and families on

how to perform and assist with certain activities. LOF, activity attempts/completion, and adverse safety events will be recorded on an EM flowsheet. The intervention will start while the patient is in the CICU and will continue until discharge from the CICU.

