To introduce the EM protocol to the nursing staff, the nurse and physician champion will provide a series of in-service training sessions. Physicians routinely caring for older adults in the CICU and rotating trainees will receive education in the CICU through “Lunch and Learn” conferences. Weekly audits will be performed by the nurse champion to assess for adherence to the EM protocol. Reminders and further education will be provided if necessary. Monthly status reports will be created and disseminated to the nurses and the CICU team.

Frailty will be assessed on admission using the Clinical Frailty Scale (CFS) by the patient’s nurse or a member of the research team (Appendix B).³² The CFS is a simple bedside assessment tool that uses a single global judgement-based measure to assign a score from 1 (very fit) to 9 (terminally ill) with increasing scores from 5 to 8 indicating more advanced frailty.²⁰ The CFS correlates with more comprehensive frailty tools, has been shown to accurately diagnose frailty in critically ill and acute cardiac populations, and provides short and long-term prognostic information.^{20, 21, 33}

Enrolled participants will be approached to participate in this prospective substudy. Patients accepting participation will be asked to wear an accelerometer monitor during CICU stay until the end of hospitalization to capture the time spent in each mobility position. Body composition parameters including skeletal muscle mass and fat mass will be measured daily with a segmental multi-frequency bioimpedance scale.

Instruments

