In the patients wearing the accelerometer, data will be recorded on the total time spent in each mobility position, the daily average time spent in each mobility position, the average duration of time for each bout of sitting, standing, and walking, and sleep duration. The step count will also be recorded. The change in skeletal muscle mass from CICU admission to hospital discharge will be recorded.

We will determine which covariates predict improvement in LOF (“responsiveness”) and which ones do not (“non-responsiveness”). We will assess the recovery of physical function at 1 month and 12 months as measured by the SF-36 physical component summary score. We will compare the SF-36 scores of the highest scoring tertile of LOF on hospital discharge with the lowest scoring tertile. We will also compare hospital readmission at 30 days and discharge home vs. healthcare facility.

For safety, we will record the composite and individual components of the number of falls, injuries, and dislodgements over the total number of attempted mobility activities. The results from the intervention cohort will be compared to the pre-intervention cohort for all results.

Data Collection Procedures

Following discharge, a member of the research team will capture the following hospitalization data from the electronic medical record (Chartmaxx, Quest Diagnostics, Madison, New Jersey) for each subject: age, sex, primary admission diagnosis, comorbidities, level of function assessments, CFS score, length of CICU stay, length of hospital stay, discharge location, and referral to cardiac rehabilitation.

Availability of Participants

In the fiscal year 2016-2017, there were 1,356 admissions to the JGH CICU (mean age 68 years old; 477 female (35%)). There were 1,034 patients (76.3%) age ≥ 60 years old. The mean CICU length of stay was 3.3 days and the mean hospital length of stay was 9.5 days. Only one in five patient stays was less than 24 hours in length.

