From the pilot data, we conservatively estimate that about one-third of patients will not be eligible for the study and about 70% will agree to participate. We estimate that the loss of patients to 12 month follow-up will be approximately 10% as the vast majority of CICU patients are followed by hospital-affiliated cardiologists prior to admission or are assigned to one following CICU discharge. Given these estimates, approximately 75 patients are expected to be enrolled and followed during the pre-intervention period and 300 patients are expected to be enrolled and followed during the 12 month intervention period.

Data Analysis

Since the response variable, LOF mobility, is an ordinal variable measured at different timepoints, a cumulative logit model for repeated measurements will be fitted using generalized estimating equations. The model permits us to take into consideration the structure of the correlation between the observations. The model will then be adjusted using covariates of interest, such as age, sex, EM adherence, time spent lying in bed, and illness severity score. Predictors of change in LOF during CICU stay and following hospitalization will be assessed using linear regression. Predictors of EM adherence will also be evaluated using linear regression. All statistical analyses will be performed using SAS version 9.4 by [name], a senior biostatistician affiliated with the Lady Davis Institute Center for Epidemiology.

VII. RESOURCE AVAILABILITY AND SUPPORT

The CICU at the JGH has 16 beds equipped for advanced hemodynamic support and 32 ward beds with telemetry available. Patients are admitted to the CICU mainly for acute primary cardiovascular disease.

The nurse champion's role is to attend EM team meetings, provide education to nursing and clinical partners, and ensure nursing adherence to the protocol. A review of the CICU environment conducted with physiotherapists from the EM team has ensured that the CICU is already equipped with the standard equipment necessary for patient mobilization, particularly for bedbound and immobile patients, and nurses have been trained to use the equipment.

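### The only stated analysis of discharge level of function against later SF-36 is a tertile contrast with no stated adjustment for prehospital function or frailty

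*Combined protocol and SAP*

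**What the plan says.** Section II, Hypothesis 2, reads in part: "Level of function on CICU discharge and time spent lying in bed during hospitalization is associated with health-related quality of life scores". It goes on to include functional status at longer-term follow-up.

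The link from LOF to SF-36 is taken up once, in Section VI under Outcome Measures: "We will compare the SF-36 scores of the highest scoring tertile of LOF on hospital discharge with the lowest scoring tertile". No test, model or covariate is named there.

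The Data Analysis section describes three analyses:

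- A GEE model for LOF: "Since the response variable, LOF mobility, is an ordinal variable measured at different timepoints, a cumulative logit model for repeated measurements will be fitted". Its covariates follow: "The model will then be adjusted using covariates of interest, such as age, sex, EM adherence, time spent lying in bed, and illness severity score".
- A regression for LOF change: "Predictors of change in LOF during CICU stay and following hospitalization will be assessed using linear regression".
- A linear regression for predictors of adherence to early mobilization (EM).

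SF-36 is the response in none of these. The covariate list is open-ended, belongs to the LOF model, and names neither prehospital LOF nor frailty.

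Both variables are available. Under Pre-intervention in Section VI, "nurses will ascertain and record the prehospital LOF, admission LOF, and LOF on the day of CICU transfer". The Clinical Frailty Scale (CFS) is scored on admission and is among the items extracted from the record.

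The protocol also regards both as prognostic. Section IV.A states: "Older adults have a higher burden of prehospital functional impairment, which is an important predictor of morbidity and mortality". Section IV.C says frail older adults are more prone to functional decline in hospital and to long-term disability afterwards.

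**The concern.** A patient's function before admission can influence both LOF at discharge and how that patient scores on the SF-36 months later. By the protocol's own account, frailty acts on in-hospital decline and on later disability, so it sits on both sides of the contrast. SF-36 is planned only at 1 and 12 months, so there is no baseline score to adjust for or subtract. Prehospital LOF and CFS are the natural stand-ins, and the plan does not bring them into this analysis.

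What is at stake is interpretation. If the top tertile scores better, the plan as written gives no way to tell whether LOF at discharge adds anything to what was known about the patient before admission. An investigator would want to know that before treating discharge LOF as a marker of later quality of life in its own right.

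**Working it through.** **The plan's own figure.** No effect size, power or SD is given for this contrast. The only sample-size figure is the expected enrolment and follow-up of 75 + 300 = 375. The stated rates give 1,034 × 0.8 (stays of at least 24 hours) × 2/3 (eligible) × 0.7 (consenting) × 0.9 (followed) = 347 in 12 months and 87 in 3 months. The plan's totals are lower, but it calls its rates conservative and its totals approximate. Nothing below turns on the difference. I use the plan's 375, or 125 per tertile.

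**Inputs.**

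- From the documents: N = 375; eligible prehospital LOF limited to 3–5 (Design, participants and setting); pilot prehospital LOF mean 4.7, SD 0.6 (Section V).
- Assumed: SF-36 component score SD 10 (only the average of 50 is stated); equal correlations r of pre-admission function with discharge LOF and with SF-36; no independent effect of discharge LOF; two-sided 5% test.

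**Analytic check.** If the only link between LOF and SF-36 runs through pre-admission function, their correlation is r × r. For a normal variable, the means of the top and bottom thirds lie 2.18 SD apart. So

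difference = 2.18 × r × r × 10.

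| r | r × r | Difference (points) | Significant, 125 v 125 |
|---|---|---|---|
| 0.3 | 0.09 | 2.0 | 34% |
| 0.4 | 0.16 | 3.5 | 80% |
| 0.5 | 0.25 | 5.5 | 99% |
| 0.58 | 0.336 | 7.3 | 100% |

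For scale, the standard error is 10 × √(2/125) = 1.26 points.

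**Check within the eligible range.** A simulation (800 runs per setting, N = 375) placed prehospital LOF on 3, 4 and 5 with shares 7.5%, 15% and 77.5%. That gives mean 3 × 0.075 + 4 × 0.15 + 5 × 0.775 = 4.7 and SD 0.6, as in the pilot. Discharge LOF was ordinal with five levels.

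| r | Confounder is prehospital LOF category: unadjusted | Same, adjusted for it | Confounder is underlying function: unadjusted | Same, adjusted for LOF category and CFS |
|---|---|---|---|---|
| 0.3 | 1.9 (32%) | about 0 | 1.9 (32%) | 0.5 (8%) |
| 0.4 | 3.3 (76%) | about 0 | 3.4 (77%) | 1.1 (16%) |
| 0.5 | 4.8 (97%) | about 0 | 5.2 (99%) | 1.8 (31%) |
| 0.58 | 6.3 (100%) | about 0 | 7.1 (100%) | 2.6 (53%) |

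Cells show points, with the share of runs significant in brackets. In the third column 4–7% of runs were significant, close to the nominal 5%.

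Restricting entry to prehospital LOF 3–5 therefore does not remove the problem. Where the measured variables capture pre-admission function only in part, adjustment removes roughly two thirds of the spurious difference: 1 − 0.52/1.86 = 72% at r = 0.3 and 1 − 2.56/7.13 = 64% at r = 0.58 (unrounded results).

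**Within one cohort.** With 75 patients and prehospital LOF category as the confounder, the unadjusted difference is still 2.1 to 6.3 points, significant in 12% to 63% of runs. Splitting by cohort lowers the chance of declaring the difference but leaves the bias.

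**The case against.** The strongest reply is that Hypothesis 2 claims only an association. In every setting above, discharge LOF and SF-36 really are correlated, so a significant contrast detects something true. This stands. A reader might infer that the plan would declare a null relation significant; it would not. Only a null independent effect would be misread, and the plan does not claim an independent effect for this contrast.

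Other replies also limit the point:

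- The plan is silent on adjustment; it does not say the contrast will be unadjusted. But nothing fixes the covariates in advance, and the one covariate list is for a different outcome.
- Hypothesis 2 is wider than SF-36. Its functional-status part is served by the adjusted LOF model, so the concern covers only the quality-of-life part.
- The contrast is neither the primary outcome nor one of the five listed secondary outcomes. A reader might infer that it would be used to argue that EM works. The documents do not say so: effectiveness is Aim 3, addressed by comparing the cohorts.
- A reader might assume the tertiles pool the two cohorts. The plan does not say this, and Outcome Measures promises a cohort comparison for all results.
- A reader might infer that patients leaving with low LOF are mostly those who arrived impaired. The pilot data do not support that: among eligible patients, mean LOF was 4.7 before hospital and 2.3 on CICU admission, so acute illness plays a large part.
- The correlation of −0.580 between prehospital LOF and frailty in Section V comes from another centre, where frail patients averaged a prehospital LOF of 2.59. It relates two baseline measures and is neither of the correlations assumed above.

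None of these gives the plan a way to separate discharge LOF from pre-admission status.

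**Conclusion.** The point holds in a limited form. The tertile contrast is the only stated analysis of LOF against SF-36, it has no stated adjustment, and pre-admission function or frailty could account for part or all of what it finds. It cannot show that discharge LOF is informative beyond pre-admission status.

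The size, about 2 to 7 points, rests wholly on assumed correlations of 0.3 to 0.58, an assumed SD of 10 and no independent LOF effect. It shows what is possible and should not be read as the bias to expect; at the weak end the contrast would be significant in only about a third of trials.

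Adjustment improves matters without settling causation. Prehospital LOF is concentrated at the top of its scale in the pilot, and acute illness may also affect both LOF and later scores, so some confounding is likely to remain. This is worth correcting because the remedy is nearly free, but it does not threaten the primary outcome.

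**What to change.** Add to Data Analysis: the SF-36 physical and mental component scores at 1 and 12 months will each be regressed on in-hospital LOF, with prehospital LOF, CFS, age, sex and cohort as covariates. The adjusted LOF coefficient, with its confidence interval, is the main result for the quality-of-life part of Hypothesis 2. The tertile contrast is kept as description. Results are worded as associations with possible residual confounding.

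The same sentence should name the LOF timepoint, since Hypothesis 2 refers to CICU discharge and the tertile contrast to hospital discharge.

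The cost is a few lines of text. Prehospital LOF decides eligibility, so it must be known in both cohorts; CFS, age and sex are already extracted from the record; and cohort is known by design.

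### Safety is compared between cohorts per attempted activity, a denominator that EM is designed to raise, so the ratio can be 1 or below while events per patient rise

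*Combined protocol and SAP*

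**What the plan says.** Hypothesis 1 (Section II) reads: "An early mobilization (EM) program is safe, feasible, and effective in older adults in a Canadian tertiary care academic CICU". Aim 2 (Section III) is to assess safety and feasibility and is not worded as a comparison.

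The safety measure is in Section VI, Outcome Measures: "we will record the composite and individual components of the number of falls, injuries, and dislodgements over the total number of attempted mobility activities". The sentence after it makes the measure comparative: "The results from the intervention cohort will be compared to the pre-intervention cohort for all results". No safety measure per patient or per patient-day is stated, and Data Analysis gives no safety analysis, test or margin.

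The two cohorts are mobilized differently by design. Under Pre-intervention, nurses record LOF "but will continue usual mobilization practices". Under Intervention, "Each LOF has 3 primary activities designed to promote the patient to the next level", and "The nurse and clinical partner will attempt and/or complete each LOF activity once per shift".

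The recording routes also differ. Before EM, post-discharge record review extracts "adverse events during mobilization (falls, dislodgements, and injuries), mobilization activities". Under EM, "LOF, activity attempts/completion, and adverse safety events will be recorded on an EM flowsheet". The extraction list in Data Collection Procedures, which applies to every subject, does not include adverse events.

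**The concern.** Events per attempt answers a procedural question: how risky is one mobilization attempt? Hypothesis 1 is about the program. A patient in the program bears the risk summed over all the attempts that the program adds. When the intervention itself raises the number of attempts, dividing by attempts removes that part of its effect from the comparison.

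If events per patient doubled and attempts tripled, the planned comparison would show a lower event rate under EM, although a larger share of patients had been harmed. The other patient-level results in the plan do not fill the gap. Thirty-day readmission, discharge destination and mortality are not labelled safety and do not count falls, injuries or dislodgements.

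A second, smaller issue is ascertainment. Events and attempts come from chart review in one cohort and from a flowsheet in the other, which could bias the comparison in either direction.

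**Working it through.** The plan gives no event rate, attempt count or safety sample size, so there is no figure of its own to reproduce. The check has three steps.

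**1. The identity.** Let k be attempts per patient-day under EM divided by attempts per patient-day before EM. Then

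per-attempt event ratio = per-patient-day event ratio / k.

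For any k above 1, the per-attempt ratio is 1 or less whenever the per-patient-day ratio lies between 1 and k. At k = 1 the two ratios agree. Below 1 the distortion reverses.

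**2. What k could be.** Three activities per LOF, each once per shift, is in the plan. Shifts per day, adherence and usual attempts per day are not, so they are assumed:

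k = 3 × shifts × adherence / usual attempts per day.

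A doubling per patient-day is fully masked (per-attempt ratio 1 or less) when k is at least 2, that is, when usual attempts per day are at most 1.5 × shifts × adherence.

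| Shifts/day (assumed) | Adherence (assumed) | Doubling masked if usual attempts/day are at most | No distortion (k = 1) at |
|---|---|---|---|
| 2 | 100% | 3.0 | 6.0 |
| 3 | 100% | 4.5 | 9.0 |
| 2 | 60% | 1.8 | 3.6 |
| 3 | 60% | 2.7 | 5.4 |

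**3. A worked illustration.** From the plan (Availability of Participants): about 75 and 300 patients, a mean CICU stay of 3.3 days over all admissions, and one stay in five under 24 hours. Stays under 24 hours are excluded from the study. If those short stays average m days, with m between 0 and 1, the mean of the rest is (3.3 − 0.2m)/0.8, which is 3.875 to 4.125 days. I use 4.0, which assumes that the 2016-2017 figures carry over. Assumed: 1 event before EM and 8 under EM, each in a different patient; 2 and 6 attempts per day.

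| | Pre-intervention | EM | Ratio (exact 95% CI) |
|---|---|---|---|
| Patients with an event | 1/75 = 1.3% | 8/300 = 2.7% | 2.0 (no CI computed) |
| Patient-days | 75 × 4 = 300 | 300 × 4 = 1,200 | |
| Events per 100 patient-days | 0.33 | 0.67 | 2.0 (0.27 to 88.7) |
| Attempts | 2 × 300 = 600 | 6 × 1,200 = 7,200 | |
| Events per 1,000 attempts | 1.67 | 1.11 | 0.67 (0.09 to 29.6) |

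Here k = 6/2 = 3, and 2.0/3 = 0.67, as the identity requires. The rate-ratio intervals condition on the nine events. The difference in proportions is +1.3 percentage points, with an exact unconditional 95% CI of −5.1 to +4.4.

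**The case against.** The strongest reply has four parts.

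- **Events per attempt is a legitimate measure.** This stands for describing procedural risk within the EM cohort, and Aim 2 is not comparative. It does not cover the pre/post comparison that Outcome Measures then sets up.
- **The plan sets no safety test, margin or decision rule, and per-patient rates could be derived later.** This largely stands. A reader might infer that the plan commits itself to declaring EM as safe as usual care on the per-attempt ratio. The documents do not say that. But a denominator chosen after the data are seen is open to selection, and adverse events are missing from the extraction list common to all subjects.
- **At about 75 against 300 patients, neither measure settles anything.** This stands. The per-attempt interval of 0.09 to 29.6 would not let a careful reader conclude that EM is equal or safer. Imprecision is still no reason to rely on a point estimate that can have the wrong direction.
- **A per-patient count limited to mobilization-related events has the opposite weakness.** This also stands. Such a count tends to rise with the number of attempts, even if total falls and dislodgements in the CICU are unchanged. The fix has to allow for it.

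A reader might also infer that the different recording routes favour EM. The documents do not support a direction. Charts may under-record attempts or events, and the plan does not say whether the flowsheet is part of the medical record.

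**Conclusion.** The concern holds as a fault in the measure chosen for the pre/post safety comparison. The sole measure labelled safety has a denominator that the intervention is designed to increase, so its ratio can be 1 or below while events per patient rise by any factor up to the attempt ratio (at equal length of stay).

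The conclusion rests on the identity and on the plan's own description of EM against usual practice. The size is unknown, because usual attempts, shifts, adherence and event counts are all absent from the documents. A reader might infer that the plan will hide a doubling of harm. That follows only if attempts at least double, which the documents cannot confirm. If EM does not raise attempts, there is no distortion.

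The primary outcome is untouched. The point should be fixed because safety is one of the three claims in Hypothesis 1 and the repair is cheap.

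**What to change.** For the pre/post safety comparison, prespecify the following.

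1. **Main measure:** the proportion of patients with at least one fall, injury or dislodgement, as composite and by component. **Supporting measure:** events per 100 CICU patient-days. The proportion comes first because patient-days may themselves change: the Background cites shorter critical care stays with EM. If stay fell by 10% (assumed), a per-patient ratio of 2.0 would appear as 2.0/0.9 = 2.22 per patient-day.
2. **One event definition in both cohorts.** Preferably count all such events during the CICU stay. If only mobilization-related events can be captured (the list under Pre-intervention), limit the claim to those and state that this count tends to rise with attempts.
3. **The same post-discharge chart extraction in both cohorts.** In the EM cohort, count events found in either the chart or the flowsheet in the main result, so that none recorded only on the flowsheet is lost. Add a chart-only sensitivity analysis to show the effect of unequal ascertainment.
4. **Exact 95% CIs**, described as imprecise at about 75 against 300 patients.
5. **Events per attempted activity** kept as a descriptive measure of procedural risk, and not used alone to conclude that EM is as safe as usual care.

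Cost: plan wording, plus event extraction from about 300 intervention charts that are already being opened. If all events are counted, the roughly 75 pre-intervention charts also need review for events outside mobilization. This falls on a research assistant funded for 20 hours per week.

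The intervals will be wide. Even zero events in 75 patients leaves a true proportion of up to 1 − 0.025^(1/75) = 4.8% compatible with the data (two-sided 95% bound). The result is an estimate of harm per patient, not a powered test.

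### Safety is a stated hypothesis with no confidence limit or acceptable rate, and a comparison with about 75 controls cannot support it; base it on an upper limit in the EM cohort

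*Combined protocol and SAP*

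**What the plan says.** Section II (Hypotheses) states: "An early mobilization (EM) program is safe, feasible, and effective in older adults in a Canadian tertiary care academic CICU". Aim #2 in section III is "To assess the safety and feasibility of an EM program in a Canadian academic tertiary care CICU".

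The safety measure is in section VI (Methods), under Outcome Measures: "the composite and individual components of the number of falls, injuries, and dislodgements over the total number of attempted mobility activities". The next sentence gives the only inference that applies to it: "The results from the intervention cohort will be compared to the pre-intervention cohort for all results".

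The Data Analysis section covers the models for level of function and the predictors of EM adherence. It does not mention safety. No section gives a safety test, margin, confidence limit or acceptable event rate.

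On size, Availability of Participants says "approximately 75 patients are expected to be enrolled and followed during the pre-intervention period and 300 patients are expected" in the 12-month intervention period. On frequency, Background part B describes earlier critical-care studies "with only rare reports of serious adverse events and catheter dislodgement". The barriers table in section IX likewise refers to low adverse-event rates in earlier work. Neither place gives a figure.

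**The concern.** A claim of safety needs a statement of how much harm the data can rule out. The plan offers a comparison of two cohorts, and the smaller has about 75 patients. If events are uncommon, many plausible increases in harm would leave that comparison non-significant, and a non-significant result does not show that harm is absent.

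The claim will be used outside the unit. Section XII (Potential Impact) expects the study to supply evidence of safety and to encourage routine EM in other cardiovascular intensive care units. Without a criterion fixed in advance, a reader cannot tell which result would have counted against safety.

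**Working it through.** **Inputs from the documents.** About 75 pre-intervention and 300 intervention patients (Availability of Participants). Mean CICU stay of 3.3 days (same section). Three activities per level, each once per shift (Intervention).

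**Assumptions.** Share of control patients with at least one event: 1%, 2% or 3%. Fisher's exact test at two-sided 5%, counting only results in the direction of more harm under EM. Shifts per day, which the documents do not state: 2 or 3.

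**Step 1: the plan's own figure.** There is no power or safety calculation to reproduce, only the expected accrual. The stated inputs give 1,034 × 0.8 × 2/3 × 0.70 × 0.90 = 347 a year, and 347/4 = 87 in three months. These exceed the 300 and 75 quoted, which the text calls conservative. I use 75 and 300 and return to 87 and 347 in step 3.

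**Step 2: chance of no control event.** (1 − p)^75 is 47% at 1%, 22% at 2% and 10% at 3%.

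**Step 3: power of the comparison.** Sum the binomial probabilities of all outcomes (x of 75, y of 300) with y/300 > x/75 and Fisher p ≤ 0.05:

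| Control risk (assumed) | 2-fold | 3-fold | 4-fold | 5-fold |
|---|---|---|---|---|
| 1% | 0.1% | 2% | 11% | 26% |
| 2% | 5% | 21% | 43% | 67% |
| 3% | 11% | 37% | 69% | 90% |
| 5% | 21% | 68% | 94% | above 99% |

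The 5% row lies outside the assumed range and shows where the argument weakens. With 87 and 347 patients, power for a tripling is 3% at 1% and 24% at 2%, so the higher accrual changes little.

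**Step 4: what results would look like.** With 0/75 controls, 14/300 EM patients with an event (4.7%) gives p = 0.08; it takes 15/300 to reach p = 0.049. With 1/75 against 4/300 the risk ratio is (4/300)/(1/75) = 1.0. The standard error of its log is √(1 − 1/75 + 1/4 − 1/300) = 1.11, so the 95% interval is exp(±1.96 × 1.11), or 0.11 to 8.8.

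**Step 5: the planned denominator.** With 2 shifts, attempts per EM patient are about 3.3 × 3 × 2 = 19.8, so 300 patients give 5,940. A rate of 0.1% per attempt corresponds to 1 − 0.999^19.8 = 2.0% per patient. An exact conditional Poisson test, treating attempts as independent, has 16% power for a tripling if controls have as many attempts per patient, and 0.1% if they have half as many. With 3 shifts these are 32% and 6%. At 0.5% per attempt with equal attempts, power for a tripling is 92% (2 shifts) or 99% (3 shifts).

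**Step 6: what the EM cohort can show alone.** The Clopper-Pearson two-sided 95% upper limit for x of n is the 0.975 quantile of Beta(x + 1, n − x). For n = 300:

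| Patients with an event | Observed | Upper limit |
|---|---|---|
| 0 | 0% | 1.2% |
| 3 | 1% | 2.9% |
| 6 | 2% | 4.3% |

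For comparison, 0 of 75 gives an upper limit of 4.8%.

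**The case against.** The strongest reply is that the plan never says non-significance means safe. It names no test and no alpha. A reader might infer that following the plan leads to a finding of no difference and hence of safety, almost whatever EM does. The documents do not support that: the rule is not there, and the power figures rest on an assumed conventional test. This stands.

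A reader might also infer that the plan ignores the EM cohort's own safety data. It does not. The event rate per attempted activity can be computed in that cohort as planned. What is missing is its interval and an acceptable value.

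Third, rarity is easily over-read. In Background part B the word applies to serious adverse events and catheter dislodgement in earlier studies. The composite here also contains falls and injuries of any grade, and section IV.D says it is unknown whether earlier findings carry over to the CICU. The 1% to 3% range is therefore an assumption. Within it, 4- and 5-fold rises at 3% would probably be detected. A claim that any several-fold rise would be missed is too strong.

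Finally, safety is neither a primary nor a secondary outcome. It is, however, part of Hypothesis 1 and Aim #2, so it still needs a criterion. None of these replies supplies one, and none makes the comparison informative about a doubling or tripling of an uncommon event.

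**Conclusion.** The point holds in this form: safety is a hypothesis without a confidence limit or acceptable rate, and the cohort comparison cannot support it. At assumed control risks of 1% to 3% per patient, a doubling would be missed about 89% to 99.9% of the time and a tripling about 63% to 98%. The conclusion weakens if events are commoner: at 5% per patient, or 0.5% per attempt with equal attempts in both cohorts, a tripling would probably be seen.

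The comparison has a further weakness that power does not capture. Pre-intervention events and activities are extracted from the medical record after discharge, while intervention attempts and events are entered on a flowsheet, so a ratio of the two rates may partly reflect recording.

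This should be changed, because a better analysis of the same data is available at little cost.

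**What to change.** Add to Data Analysis:

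- Keep the planned event rate per attempted mobility activity, composite and by component, with a 95% interval that allows for clustering of attempts within patient.
- Beside it, report the proportion of EM patients with at least one mobilization-related event, with its exact (Clopper-Pearson) two-sided 95% confidence interval. State the sidedness: for 0 of 300 the upper limit is 1.22% two-sided but 0.99% as a one-sided 95% limit.
- Base the safety conclusion on that two-sided upper limit falling below a ceiling that the EM team sets and justifies before the first intervention patient. The value is theirs to choose.
- Report the comparison with the pre-intervention cohort as descriptive, with its confidence interval, and say that it is not evidence of safety.

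This costs a few sentences and one agreed number, with no extra patients or data collection. The downside is that safety may fail to be shown: with 6 of 300 patients affected, for example, any ceiling of 4.3% or lower would not be met.
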